3. Exploratory Aim: Describe the pharmacological and non-pharmacological strategies Veterans are using to manage pain and their perceived helpfulness. This will provide insights into the effects of the current opioid restrictions on pain management strategies. These strategies & their perceived helpfulness will be assessed using the Pain Management Strategies Survey at baseline, 6 weeks, 3, and 6 months.

Study Design

The proposed study is a multi-site, double-blind, two-arm, parallel, randomized controlled trial. At-risk Veterans will be randomly assigned to one of two groups: 1) Acceptance and Commitment Therapy (ACT); or 2) Attention Control (AC). Primary and secondary outcomes will be measured at 6 weeks, 3 and 6 months but 6 months will be the primary outcome endpoint for determining mediator effects. Data collected at postoperative week 1 will be used as potential moderators of treatment response.

Schema

Inclusion and Exclusion Criteria

The target study population is veterans undergoing unilateral total knee arthroplasty (TKA) who are at-risk for persistent postsurgical pain (i.e. report moderate to severe preoperative pain in the presence of anxiety and/or depression OR report severe pain and absent anxious and depressive symptoms). A total of 430 participants (215 per group) will be recruited to achieve 150 subjects per group.

Inclusion Criteria

Participants must meet all the following inclusion criteria to participate in this study:

- Veteran;
- 18 years old or older;
- Having unilateral total knee arthroplasty (TKA);
- At risk for pain, anxiety, depression and/or stress, or pain catastrophizing defined as 1, 2, 3 or 4 (below):
 1. Worst pain greater than or equal to 7 on BPI (severe pain)
 2. Worst pain 3-6 (moderate to severe pain) on BPI AND anxiety symptoms (anxiety score greater than or equal to 6 on the DASS 21 or DASS stress score greater than or equal to 10)
 3. Worst pain 3-6 (moderate to severe pain) on BPI AND depressive symptoms (depression score greater than or equal to 7 on the DASS 21)
 4. Worst pain 3-6 (moderate to severe pain) on BPI AND PCS score greater than or equal to 20

Exclusion Criteria

All candidates meeting any of the exclusion criteria will be excluded from study participation.

Exclusion criteria are:

- Inability to complete study forms because of language/literacy barrier;
- Bipolar or psychotic disorder;
- History of brain injury (moderate to severe TBI, other severe injury);

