For variables in the primary aim (pain severity and functioning), efficacy of ACT compared to AC at 6 weeks, 3 months and 6 months will be tested using linear mixed model analysis for repeated measures. The fixed effect in the model will include intervention group, time, and intervention*time interaction effect. The model will also include site, workshop (cluster) within intervention, and subject as random effects. Test of mean contrast will be used to compare between treatment group means and mean change from baseline to 6 weeks, 3 and 6-months post-TKA between ACT and AC. P-values will be adjusted using Bonferroni's method to account for the number of tests performed. The efficacy of ACT versus AC will be expressed as the group mean difference with a 95% confidence interval (CI), using the SAS STAT (14.1) MIXED procedure.

For the secondary aim (A), efficacy of ACT compared to AC on anxiety symptoms, depressive symptoms, pain acceptance, and engagement in values-based behavior will be compared using linear mixed model for repeated measures. Intervention group mean differences will be estimated and tested as described in the analysis for the Aim1 variables.

For the primary and secondary aim analyses, it is expected that randomization will lessen the need for covariate or moderator adjusted analyses. However, if any demographic, baseline, time from workshop to surgery, or perioperative variables (i.e. perioperative anesthesia/analgesic, postoperative complications, postop day 1 pain and function, etc.) are found to differ between intervention groups, the model will be expanded to include these variables as covariates or effect moderators to estimate and test intervention group mean differences, or odds ratio, controlling for these variables.

In addition to the analyses described above for the primary & secondary outcome measures, similar linear mixed model analyses that include all randomized subjects will be performed. This secondary analysis will include surgery status in the model to contrast the impact of the intervention on those with and without surgery.

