For the exploratory aim, frequencies for each pharmacologic and non-pharmacologic pain management strategy will be calculated to describe the types of strategies reported at each visit. Patterns (from baseline to 6 months) and trends (i.e. changes over the 4 year data collection period) will be examined. Helpfulness ratings will be averaged using means and standard deviations or medians and interquartile ranges for each strategy to provide insights on strategies at-risk Veterans find helpful. Differences in types and helpfulness of pain management strategies by treatment group will be explored.

Sample Size

Sample size was estimated using KOOS-Activities of Daily Living Subscale (the primary outcome requiring the largest sample size). According to the literature, a change of 8 points or more represents a clinically significant improvement.⁸⁵ Therefore, assuming an average of 6 participants per workshop (cluster), with an ICC of 0.06 and a standard deviation of 18, a sample size of 300 Veterans (n=150 per treatment group) will be needed to detect a clinically

significant difference of 8 at a 0.0167 significance level (adjusted for testing at 3 time points) with 0.80 power. Assuming 20% will have surgery cancelled/postponed due to health issues and 10% will drop out after randomization (17% and 10%, respectively, was observed in our R34 study), we plan to enroll 430 Veterans to ensure that we will have $n=150$ per treatment group for the primary aim analyses. Veterans who do not have surgery after randomization will be followed over a similar timeframe and will be included in the secondary analyses.

Recruitment, Consent and Enrollment

Summary of recruitment and consent process, in-person

Identifying Patients

In order to increase awareness of the study, flyers describing the study will be posted in the orthopedics clinic and copies will be made available for patients to take. The study's Research Assistant (RA) will use Vista to identify all patients scheduled in the VAMC Orthopedics Clinic for a knee pain consultation. The RA will then review these patients' medical records to determine if they speak English with adequate competence AND do not have a diagnosis of dementia, bipolar or psychotic disorder, or history of brain injury. They will also review prior orthopedic notes to gauge readiness for surgery.

Approaching Patients

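### Holm's step-down method would hold the same family-wise error as the planned Bonferroni adjustment and give more power when ACT works at more than one visit

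*Combined protocol and SAP*

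**What the plan says.** The primary aim compares ACT with attention control at 6 weeks, 3 months and 6 months on BPI Pain Severity, KOOS ADL and KOOS QoL, using a linear mixed model for repeated measures. Of the comparisons, the Data Analysis section of the Précis says: "Test of mean contrast will be used to compare between treatment group means and mean change from baseline to 6 weeks, 3 and 6-months". It then says: "P-values will be adjusted using Bonferroni's method to account for the number of tests performed". Each effect is reported as a group mean difference with a 95% confidence interval, and the text does not say that this interval is simultaneous. Secondary aim A takes over the same estimation and testing by reference.

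The Sample Size section uses the same adjustment. It sizes on KOOS ADL for a difference of 8, "at a 0.0167 significance level (adjusted for testing at 3 time points) with 0.80 power", "assuming an average of 6 participants per workshop (cluster), with an ICC of 0.06 and a standard deviation of 18". The result is 300 analysable Veterans, 150 per group. The documents mention no stepwise procedure and give no reason for preferring a single-step one.

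**The concern.** Single-step Bonferroni tests every visit at 0.05/3 = 0.0167, whatever the other visits show. Holm relaxes the level for the remaining tests once one has been rejected. It does so without an assumption about correlation and without raising the family-wise error.

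The aim asks about three postoperative visits, and the rationale is that ACT prevents persistent pain by helping Veterans cope after surgery. An effect at several visits is therefore a natural expectation, and that is the setting in which the two methods differ. At stake is the power to declare benefit at a given visit, such as 6 months, or at all three, from the same data.

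**Working it through.** **1. Reproduce the plan's sample size.** Inputs from the Sample Size section: difference 8, SD 18, ICC 0.06, 6 per workshop, alpha 0.0167, power 0.80. Sidedness is not stated, so two-sided is assumed.

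- Design effect: 1 + (6 - 1) x 0.06 = 1.30.
- Normal approximation: n = 2 x (18/8)² x (2.394 + 0.842)² = 106 per group. Then 106 x 1.30 = 138 per group, or 276 in total, which is below 300.
- t-test on workshop means with k whole workshops of 6 per arm and df = 2(k - 1): for k = 25 (150 per group), SE = 18 x √(2 x 1.30/150) = 2.370. The noncentrality is 8/2.370 = 3.376 on 48 df, and power is 0.811. For k = 24 (144 per group), power is 0.791.

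So 150 per group is the smallest whole-workshop size that reaches 0.80 at the Bonferroni level. The plan's figure reproduces, and Bonferroni causes no shortfall for three tests.

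**2. The two rules for three tests.** Bonferroni rejects each p-value at or below 0.0167. Holm orders the p-values and compares the smallest with 0.05/3 = 0.0167, the next with 0.05/2 = 0.025 and the largest with 0.05, stopping at the first failure. Two facts follow without simulation:

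- Anything at or below 0.0167 passes every Holm step, so Holm rejects all that Bonferroni rejects.
- Holm's first step is the Bonferroni test of the smallest p-value. The chance of at least one rejection is therefore identical, and so is the family-wise error when all nulls are true.

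**3. Size of the gain.** Simulation with 200,000 trials of three correlated z statistics. Where the planned effect of 8 is present, the noncentrality is z(1 - 0.05/6) + z(0.80) = 2.394 + 0.842 = 3.236, so that Bonferroni power per visit is the planned 0.80. The correlation between visits is not in the documents; 0.3 to 0.8 is assumed.

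| True effect | Quantity | Bonferroni | Holm |
|---|---|---|---|
| Planned effect at all three visits | power per visit | 0.80 | 0.85-0.87 |
| Planned effect at all three visits | power for all three | 0.57-0.69 | 0.75-0.81 |
| Planned effect at all three visits | at least one visit | 0.90-0.97 | 0.90-0.97 |
| 3 and 6 months only | power at each of these | 0.80 | 0.82-0.83 |
| 6 months only | power at 6 months | 0.80 | 0.80 |
| Fading: 8, 6, 4 | power at 6 months | 0.22 | 0.32-0.35 |
| Half the planned effect at all visits | power per visit | 0.22 | 0.25-0.26 |
| None (correlation 0.5) | family-wise error | 0.045 | 0.045 |

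**4. Check on the workshop scale.** A second simulation used workshop-level t-tests with 25 workshops per arm, correlations of 0.3 to 0.7 and 100,000 runs per scenario. With a difference of 8 at every visit, power per visit goes from 0.81 to 0.87-0.88 and power for all three from 0.59-0.67 to 0.77-0.81. The two approaches agree.

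**5. A larger family.** If the tests counted were three outcomes by three visits, alpha per test would be 0.05/9 = 0.0056. With all nine effects present (correlations 0.5 between outcomes and 0.6 between visits, assumed), power per test goes from 0.68 under Bonferroni to about 0.79-0.80 under Holm. Holm dominates for any family size.

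**The case against.** The strongest reply is that nothing is broken. Bonferroni is valid and prespecified, the analysis and the sample size both use it, and the 0.80 target is met. All of that stands. A reader might infer that the adjustment is an error or leaves the trial underpowered; the documents do not support this, because the trial was sized at 0.0167.

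A reader might also infer that Bonferroni is always less powerful. It is not. It is never more powerful, but the two methods have the same chance of at least one significant visit, and they hardly differ when only one visit has an effect. The larger gains need effects at several visits, and that pattern is unknown.

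Nor is Bonferroni without benefit. Each visit has a fixed level that carries directly into the sizing and does not depend on the other p-values, and simple matching simultaneous intervals exist (98.33% for three tests). Holm has none as simple. This weighs less here, because the plan promises only a 95% interval and does not claim simultaneous coverage.

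Finally, the number of tests in the adjustment is not defined. Sizing counts three visits, while the aim has three outcomes and contrasts both means and changes. That is a separate gap, which Holm does not close. It affects both methods, since neither can be applied until the family is known, and it leaves the dominance of Holm intact.

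**Conclusion.** The point holds as an efficiency improvement on a valid choice. For the same p-values and the same strong family-wise error, Holm is never less powerful than the planned adjustment and is more powerful when ACT works at more than one visit. With the planned effect throughout, the gain is about 5 to 7 percentage points per visit and 12 to 18 points for showing all three. It is 2 to 3 points per visit if only 3 and 6 months have the effect, and essentially nil if one visit does.

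These sizes rest on two-sided testing, a family of three, the planned per-visit power of 0.80 and assumed correlations of 0.3 to 0.8. That Holm never rejects less rests on none of these.

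**What to change.** Before unblinding, name the Holm step-down method in place of Bonferroni's method for the primary aim and secondary aim A p-values. Apply it to the same family of tests that the plan would have used for Bonferroni. Leave the sample size at 0.0167, where it remains a valid, conservative basis.

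The cost is one phrase in the Data Analysis section; the model, contrasts and enrolment do not change. The small downside is in the intervals: if multiplicity-adjusted intervals are wanted, keep them at Bonferroni width and say so, since they may then include zero for a contrast that Holm declares significant.

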- Cognitive impairment (documented in medical record and/or MIS-T score of less than 4);
- ACT therapy within the past year;
- Inability to attend workshop prior to surgery;
- Imminent risk of suicide (including recent, related hospitalization);
- Indicated surgery is revision of TKA

Termination

Participants will be terminated from the study if they do not have surgery within approximately one year of attending workshop

Re-approaching Potential Participants

Consented participants who do NOT meet inclusion criteria before their surgery may be rescreened, re-approached, re-consented and reassessed for eligibility if they are indicated to have a second TKA surgery before the end of the study enrollment period. These participants will be eligible for this reassessment no earlier than eight weeks after their first TKA.

Data Analysis

Descriptive statistics (means, medians, percentages, standard deviations, and inter-quartile ranges) of all variables will be computed for each intervention group. We will describe sex and race/ethnicity results separately to identify potential differences, based on these biological variables. The distributions of continuous variables will be evaluated for normality. If data are non-normal, statistical analyses appropriate for non-normal data will be utilized (see below). Variables will be compared across intervention groups using a t-test for continuous variables, Wilcoxon-rank sum test for ordinal and non-normally distributed continuous variables, and Pearson Chi-square test for categorical variables. Variables that are found to significantly differ between the groups will be used as covariates in the comparison of outcome measures between the treatment groups.

Intent-to-treat (ITT) analyses will be conducted to assess treatment efficacy on post-operative outcomes using all subjects that have been randomized and had surgery performed. Only those who receive surgery are included in these analyses to test the efficacy of ACT on the primary and secondary outcome measures because our underlying model for treatment effectiveness is based on the assumption that ACT will prevent the development of PPSP by helping Veterans cope with postoperative pain. Therefore, receipt of surgery is inherent in our treatment model. Follow-up data on randomized subjects that did not have surgery will be included in a secondary analyses that will contrast the effect of ACT between those with and without surgery.

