This study will use a cluster randomization approach where the unit of randomization will be the workshops. Randomization will occur right before each workshop so that all participants attending that workshop will be randomized to that intervention (i.e. ACT vs. AC). Statistician [name] will generate the randomization sequence to ensure adequate distribution of the two interventions over the study period. Randomization will be stratified by site (i.e. Iowa City versus Houston). The randomization sequence will be maintained by the Statistician in a password protected file. This file will be used to generate concealed envelopes maintained and accessed by a facilitator at each site. Allocation of workshop to intervention group will remain concealed for facilitators until approximately one week before the workshop to allow for the needed preparation. Workshop allocation to intervention group will remain concealed for all other study personnel and participants until the beginning of the workshop when all invited participants have arrived. Those in attendance will receive the assigned intervention. This allocation approach will eliminate pre-treatment withdrawals, minimize the potential for experimenter and participant bias by protecting the randomization sequence in a central location, maintain concealment of treatment allocation until the last possible moment, and keep the participants and outcome assessors blinded to treatment.

Virtual Workshops

The randomization scheme for BCM should be used for all virtual workshops.

Blinding

This is a double-blind study. Participants are blinded to which treatment is the treatment of interest and outcome assessors will be blinded to which treatment participants receive. The treatment allocators (i.e. project coordinators) and the workshop facilitators will not be blinded so they can be available throughout the study to answer questions regarding treatment. It is essential for them to know which group the participant is in, in case they need to troubleshoot the treatment.

Participants will complete the Workshop Usefulness Survey (Workshop Question 6wk) in REDCap at the end of their 6-week assessments and the Participant Blinding Question in REDCap at the end of their 6-month assessment. Assessors will complete the Assessor Blinding Question (Workshop Question 6mo) in REDCap at the end of each participants' 6-month assessment.

Post-Op Evaluations

6 Weeks, 3 Months and 6 Months Post-Op Surveys

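### Covariate rule puts post-randomisation variables into the primary and secondary efficacy models when the arms differ on them, which can bias the ACT-versus-AC effect in either direction

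*Combined protocol and SAP*

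**What the plan says.** Two paragraphs of the Data Analysis section (Précis, combined protocol and SAP) set the rule.

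- The opening paragraph lists two-group tests and then states: "Variables that are found to significantly differ between the groups will be used as covariates in the comparison of outcome measures". It does not restrict the rule to baseline variables and gives no significance level.
- A later paragraph applies the rule to the efficacy models. It begins: "For the primary and secondary aim analyses, it is expected that randomization will lessen the need for covariate or moderator adjusted analyses". It then covers the case "if any demographic, baseline, time from workshop to surgery, or perioperative variables" differ. The perioperative part of that condition reads "perioperative variables (i.e. perioperative anesthesia/analgesic, postoperative complications, postop day 1 pain and function, etc.) are found to differ between intervention groups", with the list left open. The consequence is that "the model will be expanded to include these variables as covariates or effect moderators to estimate and test intervention group mean differences".

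The Study Design section adds: "Data collected at postoperative week 1 will be used as potential moderators of treatment response".

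On timing, the Randomization section states: "Randomization will occur right before each workshop so that all participants attending that workshop will be randomized to that intervention". The workshop precedes surgery (Study Interventions). Nowhere does the plan keep an unadjusted or baseline-only model as primary, or call the expanded model a sensitivity analysis.

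**The concern.** The primary aim asks whether ACT is superior to attention control on pain and functioning after surgery. That is a total effect. Mediation is a separate question (secondary aim B) with its own method.

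A variable measured after the workshop may carry part of the workshop's effect. The plan's own rationale is that ACT works through coping with pain after surgery, and day 1 pain and function are early readings of the primary constructs. The control workshop teaches postoperative pain medication and other pain relief, so analgesic use may also differ by arm. Time to surgery has a further role: under Booster, a gap of four months or more triggers a second session, so this variable partly determines the treatment received.

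The trigger adds to the problem. A between-arm difference is what an effect of the workshop on that variable would produce, so the rule tends to adjust for the variables that treatment has moved. If unmeasured factors drive both the early variable and the later outcome, the adjusted contrast is neither the total nor the direct effect. Calling the variable a moderator does not help, because it is still post-randomisation. At stake are the meaning, the size and the p-value of the primary comparison.

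**Working it through.** **Inputs from the Sample Size section:** difference 8 KOOS-ADL points, SD 18, ICC 0.06, 6 participants per workshop, 150 per arm, significance level 0.0167 (taken as two-sided; the plan does not say), power 0.80.

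**1. The plan's own figure.** Design effect = 1 + (6 − 1) × 0.06 = 1.30. A noncentral t on workshop degrees of freedom, 2(k − 1), gives power 0.791 with 24 workshops per arm (144 participants) and 0.811 with 25 (150 participants). So 150 per arm reproduces. Enrolment also reproduces: 300 / (1 − 0.30) = 429, against 430 planned. The concern does not depend on a sample-size error.

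**2. Baseline for the illustration (normal approximation).** SE = 18 × √(2 × 1.30 / 150) = 2.37 and critical z = 2.393. Power = Φ(8 / 2.37 − 2.393) = 0.84.

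**3. Effect of adjustment once triggered.** In a linear model:

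adjusted effect = total effect − (arm effect on the early variable) × (within-arm slope of outcome on that variable).

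Let *a* be the shift in SD units and *b* the standardised slope, both assumed, with the sign set so that the shift favours ACT. The loss is *a* × *b* × 18. The covariate also explains outcome variance, so SE = 2.37 × √(1 − *b*²) × √(1 + *a*²/4).

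| *a* | *b* | Loss | Adjusted effect | SE | Power |
|---|---|---|---|---|---|
| 0.2 | 0.3 | 1.08 | 6.92 | 2.27 | 0.74 |
| 0.2 | 0.5 | 1.80 | 6.20 | 2.06 | 0.73 |
| 0.4 | 0.3 | 2.16 | 5.84 | 2.31 | 0.56 |
| 0.4 | 0.5 | 3.60 | 4.40 | 2.09 | 0.39 |

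If the control workshop is the one that improves the early variable, the sign reverses. The same inputs then inflate the estimate to between 8 + 1.08 = 9.08 and 8 + 3.60 = 11.60.

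**4. The rule as a whole, by simulation.** Settings: 150 per arm in 25 workshops, SD 18, ICC 0.06, true total effect 8, and 1,500 replicates per scenario. The analysis was least squares with workshop-robust standard errors, a simpler model than the planned mixed model. One early variable (assumed slope 0.35) was added when its arm difference had p < 0.05; that threshold is also assumed.

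| Assumed shift (SD) | Rule fires | Mean estimate | Power | Mean estimate, common cause | Power, common cause |
|---|---|---|---|---|---|
| 0 | about 5% | 8.0 | 0.83 | 8.0 | 0.82 |
| 0.2 | about 40% | 7.2 | 0.73 | 6.9 | 0.72 |
| 0.35 | about 85% | 5.9 | 0.56 | 5.0 | 0.44 |
| 0.5 | about 99% | 4.9 | 0.37 | 3.4 | 0.20 |

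The common-cause columns add an assumed unmeasured factor that affects both the early variable and the outcome. Without adjustment, the mean estimate stayed near 8.0 and power was 0.80-0.83 in every row.

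**5. Type I error.** With a true total effect of zero and the early variable shifted by 0.2-0.5 SD, the rule rejected in about 3% to 14% of trials without a common cause and about 4% to 37% with one, against a nominal 1.67%. These scenarios need a direct effect that offsets the shifted path, and the mean estimates lay on the side against ACT (−0.8 to −4.6 points). With no shift, rejection stayed near nominal (1.1% to 1.5%).

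**The case against.** Four arguments on the other side have force.

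- **Not every listed variable is moved by arm.** The documents show no route from a preoperative workshop to the type of anaesthetic, and a surgery date may already be fixed. With about 25 workshops per arm, chance imbalance is plausible, and step 4 shows little bias from adjusting for it. This stands, and it limits the concern to variables that a workshop can affect. The rule does not separate the two kinds.
- **Early pain may never reach the model.** The survey schedule covers baseline, 6 weeks, 3 months and 6 months. No listed instrument collects day 1 or week 1 pain or function. Daily logs are mentioned under missing-data strategies, but their content is not described. This stands as doubt about implementation. Complications, however, are collected in the 6-week survey and are named in the rule.
- **The rule is conditional.** At a 0.2 SD shift it fires in about 40% of simulated trials, and the mean estimate is 7.2, against 6.7 if adjustment were certain. This stands.
- **The week 1 moderator sentence does not itself alter the primary model.** This also stands; a label is enough there.

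A reader might go further and infer that adjustment removes the ACT effect, or always pulls it towards zero. The documents do not support either. Complete removal is an extreme case, and the control workshop's pain-medication content makes inflation possible too. A reader might also put power as low as 0.70-0.30 over the same assumptions. That range holds the SE at 2.37 and so ignores the outcome variance that the covariate explains.

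**Conclusion.** The concern holds in a bounded form. As written, the plan directs variables that arise after randomisation into the primary and secondary efficacy models when the arms differ on them, and it designates no other model as primary. For variables that either workshop can move, this can attenuate, inflate or otherwise bias the total effect and can distort type I error.

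The size is unknown: the documents give neither a shift nor a slope. The illustrative loss of 1.1-3.6 points, with power of 0.74-0.39 in place of 0.84, applies when adjustment is triggered. It rests on the assumed ranges for *a* and *b*, a linear model, a two-sided test and the normal approximation. The simulated averages also depend on the assumed p < 0.05 trigger and on a single early variable with no workshop-level correlation of its own. The case for changing the rule does not depend on these values, because a primary estimate should not change its meaning according to what is observed after treatment.

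**What to change.** 1. In both Data Analysis paragraphs, replace the difference-triggered rule with a closed, prespecified list of covariates measured before randomisation. Use it in the primary and secondary models whatever imbalance is observed. Both paragraphs need the change: amending only the later one would leave the unrestricted rule in the opening one.
2. Remove time from workshop to surgery and all perioperative and postoperative variables from those models, both as covariates and as moderators. Report them by arm, or in analyses labelled exploratory.
3. In Study Design, label the week 1 moderator analysis exploratory and state that it does not enter the primary model.

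The cost is a wording amendment. The sample size stays at 150 per arm, and no data collection is added. Adding perioperative variables to the secondary aim B mediation model would be a larger change, because that aim names its mediators and measures them at 6 weeks and 3 months. This fix does not require it.
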